**TARGET-PD**

these assessment methods including: no assessment during activities of daily living, poor visibility of compliance with medications, inadequate recall and/or reporting of symptoms, no or poor data quality control and inter-rater variability.

Wearable technologies have been developed in response to the lack of objective measurement tools for movement disorders symptoms and are being used in the clinical care of Parkinson's patients. Recent studies have suggested that the use of wearable sensors can inform medication choices in a clinical trial setting and correlate with relevant clinical assessment scales.

A recent study by Farzanehfar, *et al.* demonstrated that the use of objective targets and measurement with the PKG® system significantly improved clinical care and quality of life for people with PD. For the first time, this study provided clinicians with objective and continuous information to help calibrate their treatment recommendations in a timely method. The study included 103 PD patients from the Northern part of Tasmania, Australia, with low levels of access to specialist care.

Key findings of this study included:

- Most people with PD (78%) were living with excessive symptoms that were out of target, including high levels of bradykinesia (slowness and freezing), dyskinesia (involuntary movements) and tremor (constant shaking).
- With the use of objective measurements and targets reported with the PKG® system, management was improved in more than half (58%) of the 77 participants who completed the study.
- Most significantly, PKG monitoring and use of targets led to changes in oral medication, which improved quality of life and clinical outcomes of 43% of patients who completed the study (33 patients):
  - 10-point improvement in quality of life as assessed by the PD Questionnaire (PDQ-39) ( $p < 0.08$ ).
  - 8-point improvement in clinical symptoms as measured by Total UPDRS clinical scale ( $p < 0.0009$ ).

Additionally, in 2018, two panels of movement disorder specialists published expert opinion manuscripts that serve as a basis for objective measurement to be incorporated into clinical practice guidelines. Both expert groups developed treatment targets for the management of bradykinesia, dyskinesia and motor fluctuations. These therapeutic targets will be evaluated in this study.

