#### 4.5 Interim Follow-Up Visits

Interim follow-ups will be completed for subjects who are not considered to be controlled. For PKG- group subjects, controlled means per clinician standard of care assessment and for PKG+ group subjects, this is per the Acceptable Target Range:

	Target Range
Bradykinesia Score (BKS)	Median BKS 23-25 and/or FDS > 7.5
Dyskinesia Score (DKS)	Median DKS 7-9 and FDS < 13

Interim visits can be completed in-clinic or remotely via telephone per institutional requirements. This timeframe may vary depending on a variety of factors such as physician care practices, amount of total medication change needed, subject medication regimen compliance and subject tolerance to medication changes.

Approximately 28 days prior to each planned subject follow-up visit, a PKG Watch will be ordered through the GKC Portal and dispensed to each subject as previously described and PKG report obtained prior to the visit of PKG+ group subjects for investigator review.

For subjects in the PKG+ Group, the site staff will ensure the PKG is available prior to the Interim Follow-up Visit. Protocol required data collection will occur at each follow-up interim visit. A Subject "ON" State Assessment will be completed and changes in medical history and medications will be recorded. Any protocol defined AEs that have occurred will be captured on the AE Reporting CRF (see Section 8). The study investigator will review the PKG provided by GKC prior to the visit and use the information to guide the discussion with the subject during the clinical assessment. PKG results will be recorded in the PKG Reporting CRF. The study investigator will complete the Clinician Assessment CRF to denote patient-reported symptoms, treatable findings, and clinical management planning based on his/her routine clinical assessment procedures along with the PKG information.

For subjects in the PKG- Group, protocol required data collection will occur at each follow-up interim visit. A Subject "ON" State Assessment will be completed and changes in medical history and medications will be recorded. The study investigator will complete the Clinician Assessment CRF to denote patient-reported symptoms, treatable findings, and clinical management planning based on his/her routine clinical assessment procedures. The study investigator will be blinded to the PKG information during interim visits.

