### 5.3 Ancillary Endpoints

Ancillary endpoints will include measurements as indicated below:

- Rate of protocol defined adverse events affecting health care utilization including: hospitalizations, emergency department, urgent care or unanticipated clinic visits from baseline to 4 months, 1, 2, 3 years follow-up
- Rate of protocol defined adverse events and potential contraindications for increasing dopaminergic therapy including: falls, orthostatic hypotension, bothersome hallucinations, delirium, and impairment that prohibits interaction with the PKG watch from baseline to 4 months, 1, 2 3 years follow up
- Rate of enrolled subjects in PKG + group who are unable to be brought into Target Range through follow-up visits

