3.1. Primary Objective

This is a randomized controlled trial (RCT) to evaluate treating uncontrolled patients with Parkinson’s Disease (PwP) to a target range established by published expert opinion. The study aims to evaluate clinical patient outcomes, quality of life measures and health care utilization of those patients specifically treated to a target range when using the PKG data in the clinical management of Parkinson’s disease (PD) in routine clinical care (treatment group) compared to those managed with medical history and clinical evaluation alone (control group) performed by a neurologist experienced in PD management. Both groups will be recommended to undergo medication changes until they reach a “controlled state” that is determined by either the clinician using standard of

care (SOC) (PKG- Group) or using PKG based targets and SOC assessments (PKG+ Group). For subjects in the treatment arm (PKG+ Group) the references will be according to the following table for purposes of analysis using PKG scores. Subjects will either be considered bradykinetic (BKS scores exceed targets; BKS >25) or Dyskinetic (DKS scores exceed targets; DKS >9):

	Target Range
Bradykinesia Score (BKS)	Median BKS 23-25
Dyskinesia Score (DKS)	Median DKS 7-9

The main objective of this study is to evaluate whether PwP who are managed with the aid of objective measurement and use of target ranges have improved PD symptoms and outcomes as compared to individuals treated using only standard of care (medical history, neurological examination).

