An additional analysis will be conducted due to impacts from COVID-19 for the primary endpoint. This will include looking at instances where a partial UPDRS Part III was collected due to restrictions when conducting a telehealth video visit.

Subgroup Analysis of Primary Endpoint

Subgroup analyses will be conducted to examine the possible influence of baseline characteristics on the primary outcome. Subgroups of interest may include but are not limited to:

- Duration of disease – defined by years of disease (Date of Visit 1 - Year of PD Diagnosis)
- Stage of PD - defined by Hoehn & Yahr (1-5) at Visit 1
- History of fluctuation – defined by patient wearing off in last 30 days at Visit 1
- Gender
- Age – defined by Date of Visit - DOB
- Controlled PD at Baseline Visit in PKG+ and PKG- groups as defined by the PKG for both groups.
- Uncontrolled PD at Baseline Visit in PKG+ and PKG- groups as defined by the PKG for both groups.

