- Dyskinesia Score
- Fluctuation Score
- Percent Time Immobile (PTI)
- Percent Time Tremor Present (PTT)

Evaluation of individual patient and subgroup response from baseline assessed by change in PKG BK or DK scores from baseline to 4 months for controlled (in target range) and uncontrolled (out of target range) in PKG+ and PKG- groups

- Rate of subjects who were uncontrolled at baseline (PKG Summary Scores exceeded targets) and then became controlled at the 4-month visit (PKG Summary Scores reduced to below targets).
- Rate of subjects unresponsive to medication changes (i.e. no change to PKG BK scores with LED increase)
- Rate of subjects who required treatment changes but were unwilling to make changes (this group may not show any impacts to outcomes)
- Rate of subjects who required treatment changes but were contraindicated to make changes (this group may not show any impacts on outcomes)

8. Change in LED from baseline to each interim visit and 4 months

Calculation of Levodopa Equivalent Dose (LED) at each visit for each patient and a comparison of change in LED at each visit for each patient. If a change is made at the scheduled visit, the change is calculated for the next visit (e.g., a change at the BL visit means the subject has started taking the new medication/dose/frequency change the day after the BL visit, etc.) – See Appendix for reference in calculating LED.

Rate and change in PD medications including medication type, dosing, increase, decrease from baseline to interim1, interim2, interim3, and 4 months.

An analysis to look at medication change amount and frequency and impact on outcome of MDS-UPDRS and PKG BKS will be performed. Patients will be ranked by amount of LED change at each visit and grouped by number of times they had medication changes at a visit (e.g. 0, 1, 2 times, etc.) from baseline to the 4 month visit and correlated to the outcome of MDS-UPDRS and PKG score of BKS at 4 months.

- Rate of subjects who were marked as uncontrolled but had no medication changes will be noted.
- Rate of subjects who had medication changes but were less than 100mg LED will be noted.

9. PKG Patient Survey at 4 months

PKG Patient Survey at 4 months. Tabulate values and proportions and changes from baseline to each visit.

The rate at 4 months will be calculated for the PKG+ and PKG- groups for each section of the survey.

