3.5. Ancillary Endpoints

Ancillary endpoints will include measurements as indicated below:

- Rate of protocol defined adverse events affecting health care utilization including: hospitalizations, emergency department, urgent care or unanticipated clinic visits from at 4 months
- Rate of protocol defined adverse events and potential contraindications for increasing dopaminergic therapy including: falls, orthostatic hypotension, bothersome hallucinations, delirium, and impairment that prohibits interaction with the PKG watch at 4 months
- Rate of uncontrolled subjects in PKG+ group who are unable to be brought into Target Range through follow-up visits ($BKS \leq 25$ or $DKS \leq 9$). This will also be run for a threshold of a PKG score of $BKS \leq 26$ at 4-months.

4. Study Design

This is a prospective, multi-center, single-blind randomized (1:1) controlled, longitudinal follow-up study (1, 2, 3 years).

This is a randomized controlled trial (RCT) to evaluate treating uncontrolled patients with Parkinson's Disease (PwP) to a target range established by a published expert opinion manuscript. The study aims to evaluate clinical patient outcomes, quality of life measures and health care utilization of those patients specifically treated to a target range when using the PKG data in the clinical management of Parkinson's disease (PD) in routine clinical care (treatment group) compared to those managed with medical history and clinical evaluation alone (control group) performed by a neurologist experienced in PD management. Both groups will be recommended to undergo medication changes until they reach a "controlled state" that is determined by either the clinician using standard of care (SOC) (PKG- Group) or using PKG based targets and SOC assessments (PKG+ Group). For subjects in the treatment arm (PKG+ Group) the references will be according to the following table for purposes of analysis using PKG scores*:

	Target Range
Bradykinesia Score (BKS)	Median BKS 23-25
Dyskinesia Score (DKS)	Median DKS 7-9

The main objective of this study is to evaluate whether PwP who are managed with the aid of objective measurement and use of target ranges have improved PD symptoms and outcomes as compared to individuals treated using only standard of care (medical history, neurological examination).

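### SAP 3.5 defines in range as BKS ≤25 or DKS ≤9, which is not the complement of the SAP's out-of-target rule; on two of three readings this can understate the ancillary failure rate

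*SAP*

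**What the plan says.** SAP 3.5 lists as its third ancillary endpoint the "Rate of uncontrolled subjects in PKG+ group who are unable to be brought into Target Range through follow-up visits". A parenthesis follows with the limits BKS ≤25 or DKS ≤9. The SAP then adds a second run: "This will also be run for a threshold of a PKG score of" BKS ≤26 at 4 months. It does not say what happens to DKS in that run.

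SAP 3.1 sets the out-of-target state: "Subjects will either be considered bradykinetic (BKS scores exceed targets; BKS >25) or Dyskinetic (DKS scores exceed targets; DKS >9").

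The protocol's version of the endpoint (Protocol 5.3) is "Rate of enrolled subjects in PKG + group who are unable to be brought into Target Range through follow-up visits". It contains no *or* rule. Protocol 4.5 defines being controlled by reference to the range: "for PKG+ group subjects, this is per the Acceptable Target Range". The table there has one row for BKS and one for DKS, each with an added condition on the fluctuation score (FDS).

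SAP 3.4 item 7 plans a related rate: "Rate of subjects who were uncontrolled at baseline (PKG Summary Scores exceeded targets) and then became controlled at the 4-month visit". It describes control as the summary scores having fallen below their targets, in the plural, without saying whether one score or both must qualify.

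**The concern.** The endpoint is meant to show how often treating to target fails in the PKG+ group. Out of target means that either score is too high, so being brought into range should mean that neither is. SAP 3.5 keeps the *or* after the statement has been turned round, and the result is not the complement of SAP 3.1.

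This matters because the two scores can move in opposite directions under treatment. Lowering BKS may call for more dopaminergic medication, and Protocol 1.0 notes that such treatment can bring motor complications. A rule that looks at one score may record as a success a subject who has exchanged too much slowness for too much dyskinesia.

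**Working it through.** The plan states no figure for this endpoint, so there is nothing to reproduce. The check is logical first, then a range under stated assumptions.

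**1. The complement.** Let A be BKS above 25 and B be DKS above 9 (SAP 3.1). Out of target is A or B. Its negation is not-A and not-B, that is BKS ≤25 and DKS ≤9. SAP 3.5 prints not-A or not-B, which is the negation of A and B.

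**2. Truth table for the 4-month state (in range?), with example scores.**

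| BKS / DKS | Literal *or* | Own score, BKS high at baseline | Own score, DKS high at baseline | Both scores |
|---|---|---|---|---|
| 24 / 8 | yes | yes | yes | yes |
| 24 / 12 | yes | yes | no | no |
| 30 / 8 | yes | no | yes | no |
| 30 / 12 | no | no | no | no |

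Under the literal *or*, a subject at 30 / 8 before treatment is already in range. Under the own-score reading, a subject going from 30 / 8 to 24 / 12 is a success. A subject at 30 / 12 at baseline has two high scores, and that reading does not say which one to judge.

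**3. Direction.** Failure is P(A and B) under the literal *or*, P(own score still high) under the own-score reading, and P(A or B) under the both-scores rule. In the same subjects, each of the first two events is contained in the third, so neither rate can exceed it.

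**4. Size, own-score reading.** Suppose m of n subjects fail on their own score, and k of the others end above the other limit. The rates are m/n and (m + k)/n, so the understatement is k/n. Enrollment stopped at 41 (SAP 4.1) with 1:1 allocation (SAP 4.2), so PKG+ has 20 or 21 subjects, and the uncontrolled ones are some part of these. Each crossover is worth 1/20 = 5 percentage points at n = 20 and 1/10 = 10 points at n = 10. The documents give no value for k.

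In proportions, with own-score failure f and crossover share x among own-score successes, the addition is (1 − f)x. For assumed f of 30% to 70% and x of 0 to 20%, it runs from 0 to 0.70 × 0.20 = 14 points.

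**5. Size, literal reading.** The gap is P(A or B) − P(A and B), the share with exactly one score high. With assumed rates of 50% for A and 15% for B, independent, the literal failure rate is 0.50 × 0.15 = 7.5%. The both-scores rate is 50% + 15% − 7.5% = 57.5%. Over assumed rates of 30% to 70% for A and 5% to 25% for B, with latent correlation 0 or −0.5, literal failure is 0.2% to 17.5% and both-scores failure 33.5% to 83.7%. If nobody is above both limits, literal failure is 0%.

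**6. The added run.** If BKS ≤26 is applied alone, a subject who stays at DKS 12 with BKS 23 passes. If it only relaxes the BKS limit and keeps the rest of the parenthesis, it inherits the same *or*.

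**The case against.** The strongest reply is that the parenthesis follows the words Target Range and may simply list the two limits, so that missing either one is failure. On that reading the rule is the both-scores rule and nothing is wrong. The text does not exclude it. What stands is that the SAP does not state it, while two other readings that fit the words give different answers.

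A reader might infer that the failure rate will come out near zero. The documents do not support that. The denominator is uncontrolled subjects, and a literal *or* would place many of them in range on entry, which conflicts with the endpoint's own population. The either/or wording of SAP 3.1 makes the own-score reading more natural, and there the understatement may be nil.

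A reader might also size the effect from the earlier cohort in Protocol 1.0, where "Most people with PD (78%) were living with excessive symptoms that were out of target". That figure includes tremor, which is not part of this rule, and comes from patients with little access to specialists, whereas this trial's sites are experienced in PD. It does not transfer, and no crossover rate is given at all.

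The protocol's table does not settle the matter. Its rows carry FDS conditions, and both the protocol and the SAP print lower bounds (23 and 7) that the SAP 3.5 rule does not use. The case for *and* rests on SAP 3.1, which defines out of target by upper limits only.

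Finally, crossover is not hidden. SAP 3.4 items 2 and 7 summarise DKS change, including counts of subjects who worsen. The statistical tables in Appendix 2 were not available for this review and may hold the operational rule.

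**Conclusion.** The point holds as a minor one, with moderate confidence. The printed *or* is not the complement of the SAP's own out-of-target rule. On the literal and own-score readings the failure rate can be too low and cannot be too high relative to a both-scores rule in the same subjects. On the reading that both limits must be met, there is no error. The size cannot be found from the documents and may be zero; the figures above rest on assumed rates.

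A reader might infer that the trial's findings are tilted towards the device. That goes too far. The effect is confined to one descriptive rate in a single arm of about 20 subjects, and to the SAP 3.4 item 7 rate if the same rule is carried over. The primary endpoint, change in total MDS-UPDRS at 4 months, does not use these limits; only its subgroups by PKG control status would need a matching definition.

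**What to change.** - In SAP 3.5, define in range as BKS ≤25 and DKS ≤9 at the same visit.
- State the added run as BKS ≤26 and DKS ≤9.
- In SAP 3.4 item 7, use the same both-scores rule for becoming controlled.

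The cost is one changed word, one completed definition and one clarifying phrase. No new data are needed: the SAP already classifies subjects by PKG in both arms, for example in the subgroup "Controlled PD at Baseline Visit in PKG+ and PKG- groups as defined by the PKG for both groups". The downside is a possibly less favourable rate, which stays descriptive at this sample size. A table by arm of baseline against 4-month status would be a useful option but is not needed to correct the rule.

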## 1.0 Introduction

### *Importance of motor management in Parkinson's Disease*

Parkinson's disease is a progressive disease of the nervous system marked by tremor, muscular rigidity, and slow, imprecise movement, chiefly affecting middle-aged and elderly people. These symptoms are associated with degeneration of the basal ganglia in the brain and a deficiency of the neurotransmitter dopamine. Parkinsonism refers to the collective clinical symptoms of bradykinesia, rigidity, resting tremor, and postural and gait impairments. Accumulation of alpha-synuclein in the brain is a typical neuropathological hallmark of Parkinson's disease occurring early in the course of the disease and may predate the appearance of clinical features of the disease. Manifestations in the autonomic system controlling certain functions like heart rate, digestion, etc. may also precede motor deficits of the disease. Disease progression has been shown to be attributed to alpha-synuclein spreading from diseased to healthy cells. Individuals with Parkinson's may exhibit diverse symptoms including behavioral, autonomic, somatic, and cognitive deficits however motor impairment, specifically bradykinesia or slowed movement, is required for diagnosis.

Motor symptoms are secondary to the continued loss of dopaminergic neurons in the par compacta of the substantia nigra. Upon treatment with dopaminergic therapies, individuals may develop iatrogenic motor complications that may be controlled through adjustment of medications. Approximately 40% of patients develop fluctuations and dyskinesia within 4-6 years of treatment and 70% after long-term treatment (>9 years). Patients with fluctuations tend to have greater disease severity and disability, and those that fail to derive adequate benefit from medications report poorer quality of life. Signs and symptoms of fluctuations vary, and it is thought that they may be under-recognized by clinicians as direct observation is often impractical and patient symptom recall can be incomplete and unreliable.

Other symptoms may impact PD patients through the disease progression. Tremor is present in about 60-70% of subjects with the typical resting tremor being helpful in differentiating PD from other forms of parkinsonism. Additionally, approximately 90% of patients with PD will develop at least one nonmotor symptom, and nonmotor symptoms can be the presenting feature in PD.

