2.1 Clinical Interpretation

Bradykinesia Scores (BKS) and Dyskinesia Scores (DKS) are continuous variables. In the case of the BKS, the scores can range from movements that are made with normal acceleration to those that have very low or no acceleration. There is a correlation between the median BKS and DKS between 0900-1800 hour and clinical rating scales.

A very high bradykinesia score represents complete immobility of the logger for that 2-minute period. These periods of immobility had a 85.2% concordance with the detection of sleep by ambulatory daytime polysomnography, ( $p < 0.0001$  Chi Squared). High Epworth Sleepiness Scores (ESS) were associated with a high proportion of time immobile (PTI) throughout the day ( $p > 0.01$  Mann-Whitney). The median PTI between 0900 -1800 hours in 30 age matched control subjects was 2%, representing 10 min. PD patients had higher PTI (median 4.8%) than controls ( $p < 0.0001$ , Mann-Whitney). PD subjects with a PTI above the 75th percentile (5% or 27 min) of controls had more bradykinesia, less dyskinesia and higher PDQ-39 scores than those with PTI below this level. There was no relationship between PTI and dose or type of PD

medications. However, in 53% of subjects, PTI increased in the 30-60 min after levodopa confirming that in some subject's levodopa results in increased sleepiness.

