The PKG Watch can deliver a reminder to take PD medication by delivering a vibratory cue to the wrist. Consumption of medications is acknowledged by the subject. Some patients performed this acknowledgement repeatedly and unconsciously and this behavior is a risk marker for Impulse Control Disorder. A Response Ratio (RR) represents the number of acknowledgements/ number of doses and is expressed as a percentage. In ~75% of people with PD who had high Impulsive-Compulsive Behavior (ICB) Scores, the RR was tightly correlated with ratings of Impulsive-Compulsive Behaviors ( $r^2=0.79$ ). These patients had dyskinesia, particularly when making extraneous responses. In the other 25% who had high Impulsive-Compulsive Behavior Scores according to rating scales, the RR was low and these subjects had higher Apathy scores and low levels of dyskinesia. It was concluded that the elevated Response Ratio is a specific measure of a type of Impulse Control behavior where increased incentive salience is attributed to cues by the presence of high striatal dopamine levels, manifest by high levels of dyskinesia and that there is a second form of ICBs which occur in the absence of dyskinesia, has normal Response Ratios and higher Apathy scores and may represent prefrontal pathology.

A Fluctuation Dyskinesia Score (FDS) was produced from the PKG data by summing the interquartile range of bradykinesia scores and dyskinesia scores and expressing it as an algorithm. This FDS can distinguish between fluctuating and non-fluctuating patients with high sensitivity and selectivity and was significantly lower following activation of deep brain stimulators. The FDS following deep brain stimulation lay in a band just above the score separating fluctuators from non-fluctuators, suggesting a range representing adequate motor control. When compared with control subjects the FDS of newly diagnosed patients show a loss of fluctuation with onset of PD. The FDS was calculated in subjects whose duration of disease was known and this showed that newly diagnosed patients soon develop higher scores which either fall under or within the range representing adequate motor control or instead go on to develop more severe fluctuations. It was concluded that the FDS promises to be a useful tool for identifying patients whose fluctuations are progressing and may require therapeutic changes.

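### SAP 3.5 joins the BKS and DKS limits with an or when defining attainment of Target Range, although under SAP 3.1 exceeding either limit is out of target

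*SAP*

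**What the plan says.** SAP 3.1 sets the limits used for analysis: "Subjects will either be considered bradykinetic (BKS scores exceed targets; BKS >25) or Dyskinetic (DKS scores exceed targets; DKS >9"). Its table prints the ranges as BKS 23-25 and DKS 7-9.

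SAP 3.5 then gives an ancillary rate for PKG+ subjects who were uncontrolled and were "unable to be brought into Target Range through follow-up visits ($BKS \leq 25$ or $DKS \leq 9"). A second run follows: "This will also be run for a threshold of a PKG score of" BKS ≤26 at 4 months. It mentions no DKS limit.

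Two other places in the SAP use control as judged by the PKG. SAP 3.4 item 7 reports, in both arms, subjects uncontrolled at baseline who "became controlled at the 4-month visit (PKG Summary Scores reduced to below targets"). SAP 3.2 lists subgroups of the primary endpoint, among them "Uncontrolled PD at Baseline Visit in PKG+ and PKG- groups as defined by the PKG for both groups". Neither says whether one limit or both must be met.

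**The concern.** The trial tests treating to a range, and this rate tells the reader how often PKG+ subjects failed to get there. That matters for interpreting either a positive or a null primary result. If exceeding either limit puts a subject out of target, being in target requires that neither limit is exceeded. The wording in SAP 3.5 accepts one limit.

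As written, one data set can give different rates depending on how the programmer reads the connective. Both available readings can count as attained a subject whom SAP 3.1 would call bradykinetic or dyskinetic. The error runs towards flattering attainment, and the choice between readings would be made after the data are in.

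**Working it through.** The plan states no figure for this endpoint, so there is none to reproduce. The check is logical, followed by an illustration.

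**Inputs.** From SAP 3.1: out of target if BKS >25 or DKS >9. From SAP 3.5: in range if BKS ≤25 or DKS ≤9; denominator, uncontrolled PKG+ subjects. From SAP 4.1 and 4.2: 41 enrolled, 1:1.

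**Step 1, complement.** Not (BKS >25 or DKS >9) = (BKS ≤25 and DKS ≤9). Applying each rule to the four possible states:

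| Example BKS / DKS | SAP 3.1 | SAP 3.5, literal | Both limits required |
|---|---|---|---|
| 24 / 8 | in | in | in |
| 30 / 3 | out | in | out |
| 20 / 14 | out | in | out |
| 28 / 11 | out | out | out |

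The literal SAP 3.5 rule disagrees with SAP 3.1 in two of the four states, those in which exactly one limit is exceeded. Subjects in those states are uncontrolled, and so in the denominator, yet already meet the success rule.

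**Step 2, reading by baseline type.** Suppose each subject is judged only on the score that was high at baseline. A change from 30/3 to 24/12 is then a success, although SAP 3.1 calls the end state dyskinetic. A subject at 28/11 at baseline is of both types, and no rule says which score decides.

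**Step 3, the rerun.** If only BKS ≤26 is applied, 20/14 passes although DKS exceeds 9.

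**Step 4, size under the literal reading.** Let p = P(BKS >25), q = P(DKS >9), and T = p + q − P(both), the share out of target. The share of uncontrolled subjects counted as in range at entry is 1 − P(both)/T. The documents give no joint distribution, so every input here is assumed: bivariate normal scores, T from 0.50 to 0.90, p:q from 1:1 to 4:1, correlation from −0.6 to +0.6.

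- Lowest: T = 0.90, 1:1, correlation +0.6. Solving gives p = q = 0.799. P(both) = 0.799 + 0.799 − 0.90 = 0.698, and the share is 1 − 0.698/0.90 = 0.22.
- Same T and ratio: correlation +0.3 gives 0.35; zero gives 0.48.
- Zero correlation, 1:1: T = 0.50 gives 0.83; T = 0.70 gives 0.71.
- Highest: T = 0.50, 4:1, correlation −0.6. Solving gives p = 0.405 and q = 0.101. P(both) = 0.405 + 0.101 − 0.50 = 0.006, and the share is 1 − 0.006/0.50 = 0.99.

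**Step 5, one data set under three rules.** Take 20 invented subjects, each high on one score at baseline. At follow-up, 10 are within both limits, 6 are still high on their own score only, 2 have corrected their own score but are now high on the other, and 2 are high on both. The rate of subjects not brought into range is:

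- both limits required: (6 + 2 + 2)/20 = 50%
- by type: (6 + 2)/20 = 40%
- literal: 2/20 = 10%

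**Step 6, weight of one subject.** With 41 randomized 1:1, PKG+ has 20 or 21 subjects. One reclassified subject moves the rate by 1/21 = 4.8 or 1/20 = 5.0 points if all are uncontrolled, and by 1/10 = 10 points if only 10 are.

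**The case against.** The best defence is that nobody would program the literal reading. The denominator is uncontrolled subjects, and an uncontrolled subject cannot sensibly be in range already. SAP 3.1 sorts subjects into two types, so the or is most naturally read respectively: bradykinetic subjects on BKS, dyskinetic subjects on DKS. This largely stands, and it removes the large shares in Step 4. It does not settle the matter. No sentence in the SAP states the by-type rule, and that rule still misclassifies crossover and leaves both-high subjects undefined. SAP 3.1 can also be called a type label rather than an out-of-target rule, but it says in terms that these scores exceed targets.

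A reader might infer that the protocol expects crossover within the study. It does say "Upon treatment with dopaminergic therapies, individuals may develop iatrogenic motor complications", but the accompanying frequencies are over 4-6 years and beyond 9 years of treatment. They say nothing about BKS-high subjects passing DKS 9 by 4 months.

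A reader might also take BKS and DKS to be negatively correlated, which would make 48% the floor in Step 4. The protocol's statement that subjects with high immobility "had more bradykinesia, less dyskinesia and higher PDQ-39 scores than those with PTI below this level" compares groups split on immobility. It is not a BKS-DKS correlation, so positive values belong in the range.

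It is tempting to fix attainment at the 4-month visit. The endpoint is worded across follow-up visits, Protocol 4.5 ends interim visits once the subject is in range, and SAP 3.4 item 7 already reports 4-month status. Attainment at any follow-up visit is therefore a coherent endpoint, but it should be stated.

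Finally, the SAP's statistical tables are a separate attachment not seen here and may define the row.

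**Conclusion.** The inconsistency between SAP 3.1 and SAP 3.5 is real and follows from the text alone. Its effect on the reported rate cannot be computed from the documents. Under the less natural literal reading, about 22% to 99% of uncontrolled subjects would count as in range before any treatment change, on the assumptions in Step 4. Under the by-type reading, the effect is confined to crossover and both-high subjects, whose frequency is unknown.

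The consequence is limited to one descriptive ancillary rate in about 20 PKG+ subjects. The 4-month rate in SAP 3.4 and the subgroups in SAP 3.2 have their own wording and merely lack an explicit rule. The primary MDS-UPDRS comparison does not use this definition.

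A reader might go further and conclude that the both-limits rule is the correct target. The documents do not support that. It is only the complement of the SAP's own upper limits: BKS 20 with DKS 4 satisfies it while lying below both printed ranges, and the protocol's table carries FDS terms that the SAP's table omits. Those passages must be reconciled by the sponsor, and this point does not resolve them.

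**What to change.** In SAP 3.5, replace the or with and for this analysis, so that attainment means BKS ≤25 and DKS ≤9 at the same visit. Keep DKS ≤9 in the BKS ≤26 rerun. Retain the reference to follow-up visits and state whether attainment at any of them counts. Use the same both-limits rule for the 4-month transition in SAP 3.4 item 7 and for the PKG-defined baseline subgroups in SAP 3.2. Add a sentence on how the upper limits used for analysis relate to the lower bounds of the printed ranges and to the protocol's FDS terms. What that relation should be is for the sponsor, and no clinical target is proposed here.

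The cost is a few sentences and one derived variable, with no new data. The downside is that the reported attainment rate may be lower.
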